- b. Subjects on vasoactive medications will be asked to hold medication on the morning of experimental visits but to bring the medications with them to be taken after the visit.
- c. Return 3-day dietary recall
- d. IV catheter, endothelial cell collection and blood sample: Subject will lie supine and research nurse will insert venous 18 G catheter into antecubital vein.
- e. Research staff or physician will perform J wire endothelial cell collection (3 wires) via 18 G catheter.
- f. After 20 min, nurse practitioner will then obtain blood samples thru catheter:
- Lipid panel, insulin, hs-CRP, salicylate, creatinine, AST/ALT (4.5 ml blood- light green PST tube)
- Catecholamines (8 ml blood- 2 x 4 ml Na+ Hep green top tubes)
- HbA1c (4.5 ml blood- 1 x 4.5 ml lavender top tubes)
- Extra blood collected for specialized labs performed in PIs lab:

Serum: 17 ml blood-  $2 \times 8.5$  red/gray top SST tube) for interleukin-6, tumor necrosis factor-alpha.

Whole blood (17 ml blood-  $3 \times 8.5$  ml Citrate PPT tube) for mononuclear cell DNA isolation.

- f. After 15 min supine rest the following non-invasive vascular measurments are obtained by the PI and his research staff:
- 1) Radial, brachial, carotid and femoral waveforms non-invasively for PWV assessment
- 2) Carotid artery compliance using ultrasonography
- 4) Brachial artery flow-mediated dilation (FMD) with ultrasound
- 5) Brachial artery dilation after 0.3 mg sublingual nitroglycerin with ultrasound
- g. Subject escorted to the CRU Human Cardiovascular Research Lab and a physician or research staff trained in microneurography will insert needle into peroneal nerve for measurement of muscle sympathetic nerve activity
- h. Subject will meet with bionutritionist and review 3-day food record with subject
- i. Subject receives meal/snack from CRU bionutrition and then can leave
- \*\*TOTAL blood collected for Visit 3= 68 ml (~4.5 tablespoons)

Visit 4 (4.5 hours): 2nd Baseline experimental visit (Forearm Blood Flow and Microneurography)

- a. Subject comes to the CRU Human Cardiovascular Research Lab in the CRU between 7-10am after 8 hour overnight fast
- b. Subject will be instrumented with upper arm venous occlusion cuffs and wrist cuffs

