for measurements of forearm blood flow using venous occlusion plethysmography c. A physician trained in brachial artery catheterization in the Human Cardiovascular Research Lab will then perform brachial artery catheterization with 27 G needle and undergo incremental infusions of saline, acetylcholine, acetylcholine + vitamin C (ascorbic acid), and sodium nitroprusside + vitamin C (see Expermental Procedures for details)

- d. Subject will be escorted to Dept of Ophthalmology in Pomerantz Bldg and have picture of retinal performed (scan takes  $\sim$ 10 min)
- e. Subject will be given snack or lunch in CRU.
- f. Subjects will be randomized in a 2:1 scheme to Salsalate or placebo
- g. Nurse will dispense 35 day supply (210 tablets) of Salsalate (dose 3000 mg/day = 500 mg tablets x  $6/\text{day} \times 35 \text{ days} = 210 \text{ tablets}$ ) or placebo
- h. Subject will take first dose of Salsalate (500 mg x 3 pills) or placebo at CRU and 2nd dose (1500 mg) at home in evening- this is Day 0

Visit 5 (45 min) ~Day 14: Subject will return to CRU for venous blood sample to measure serum salicylate (4.5 ml x 2 PST tubes: total 9 ml or ~0.5 tablespoons), Blood pressure, HR and survey of any side effects. If any side-effects/symptoms present, nurse coordinator will follow instructions as outlined in section VIII.2 "Plan for Managing Risks". Subject will receive 3-day food record booklet from CRU bionutritionist

Days 25: Coordinator or research staff will call subject in the evening to remind subject to start 3-day dietary record on days 26, 27, 28.

Visit 6 (5 hours) Betwee Day 26-34: Post-experimental visit #1 (FMD, PWV and Retina)

- a. Subject will take morning dose of Salsalate/placebo and return to CRU between Day 26 -35 for venous blood sample to measure serum salicylate, blood pressure, HR; and survey of any side effects
- b. All vascular measurements of Visit 3 will be repeated
- c. Middle cerebral artery blood flow velocity using transcranial dopper during the following protocol to measure cerebral vasoreactivity to hypercapnia:
- -After 3 min of normal breathing, subjects will perform 2, 30 second breathholds sparated by 3 min.
- -Next, After 3 min of room air breathing, 3 min of breathin 2%CO2, 3 min of breathing 4%CO2 (balanced with 21%O2 and N) will be performed followed by 3 min of room air

breathing.

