- d. Subject escorted to the CRU Human Cardiovascular Research Lab and a physician or research staff trained in microneurography will insert needle into peroneal nerve for measurement of muscle sympathetic nerve activity
- e. Subject will be instrumented with 24 hour blood pressure monitor to wear home for 24 hours. Subject will return it to the investigators when come in for Visit 7. There is no long term follow up.

Total blood collected for visit 6: 68 (~4.5 Tablespoons)

Visit 7 (3 hours) Between Day 27-35: Post-experimental visit #2

- a. Subject will take morning dose of Salsalate/placebo return to CRU on Day 27 or 28 for venous blood sample to measure serum salicylate, AST/ALT and creatinine (0.5 ml blood)
- b. All measurements from Visit 4 will be repeated
- c. Blood draw for salicylate, insulin, lipid panel, creatinine, ALT/AST (1  $\times$  4.5 ml lt green PST tube)
- d. Total blood collected for visit 7: 4.5 ml ( $\sim$ 1/3 tablespoon)

GRAND TOTAL Blood drawn over course of study: 172 ml (~11.5 tablespoons)

Screening Methods.

- a) Blood pressure, ECG. Subject will undergo resting BP in a private CRU exam room after 15 minutes of rest. BP will be measured in supine position in triplicate separated by 2 min with an automated oscillometric BP machine under quiet, comfortable laboratory conditions. All BPs throughout study will be performed in this identical manner. A resting supine 12-lead ECG will be recorded by placing 10 electrodes on chest and recording the ECG.
- b) History and Physical exam. Prior to the experimental visit (Visit 3), subjects will undergo a complete medical history and physical examination by [name] or a CRU nurse practitioner.
- c) Blood chemistries: After passing the physical exam standard blood chemistry analysis will be obtained under fasting conditions including a basic metabolic panel, lipid panel, HbA1C, complete blood count, TSH and FSH (for women only).

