Scheduled safety visit. Subjects will come in at 2 weeks for Visit 5 (approximately Day 14 depending on scheduling) and to have serum salicylate concentrations measured and to confirm no toxicity. The Research Coordinator/Nurse or research staff will review their 2 week side effect log (see attached survey) and survey subjects for any symptoms/side effects and. Subjects will also have serum salicylate concentrations measured at experimental visits 6 and 7.

- VIII.3 Does this study have a plan to have an individual or committee review combined data from all subjects on a periodic basis (such as summary or aggregate safety and/or efficacy data)?

  Yes
  - VIII.4 Describe the plan to review combined data from all subjects, such as summary or aggregate safety and/or efficacy data. Include the following:
    - Describe what data will be summarized and reviewed
    - Describe how frequently data will be reviewed.

The Data Safety Monitoring Plan will consist of a bi-annual independent review of the protocol by [name], Department of Internal Medicine, Division of Nephrology. The PI will provide a bi-annual report to the [name] summarizing the following:

- a) Data on progress of the protocol including subject recruitment, attrition, and minority involvement. Reasons for attrition or other recruiting issues
- b) Data on safety of research participants including unblinded data of serum salicylate, creatinine, ALT/AST concentrations at baseline and from safety visits, data on reasons for any dosing reductions in Salsalate that occurred, and data collected from evening telephone questionnaires for subject symptoms;
- c) Data on compliance in reporting of any adverse events
- d) Data on protocol compliance and any amendments to the protocol
- e) Data on any safety issues that occurred during the 6 month period.
- f) He will confirm that any action that results in the temporary or permanent suspension of the protocol is reported to all the appropriate monitoring bodies such as the CRR protocol committee, IRB, FDA, NIH, or other sponsor, etc.

Every 12 months, the PI will summarize outcome data and provide to [name] for review of the efficacy of treatment intervention on primary outcomes

VIII.5 Will overall safety monitoring be performed by individual(s)/committee at The University of Iowa. (NOTE: If this study involves more than

minimal risk, in most cases these should be individuals who are not members of the study research team.)?

Yes

VIII.6 List names:

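### As the schedule reads, no subject has a planned kidney or liver value on treatment before about Day 26, and two sources named for the six-monthly safety report do not match the visits

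*Combined protocol and SAP*

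**What the plan says.** **The report (VIII.4 item b).** The PI sends the independent reviewer a six-monthly summary. It includes "unblinded data of serum salicylate, creatinine, ALT/AST concentrations at baseline and from safety visits", the reasons for any dose reductions, and "data collected from evening telephone questionnaires for subject symptoms". Section XI.1 analyses no harm variable, and the separate 12-monthly summary covers efficacy on the primary outcomes. The six-monthly report is thus the only stated aggregate review of harm.

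**The safety visit (VII.E.6 and VIII.2).** VIII.2 applies its safety-visit heading to Visit 5, at about Day 14. VII.E.6 lists for that visit "serum salicylate (4.5 ml x 2 PST tubes: total 9 ml or ~0.5 tablespoons), Blood pressure, HR and survey of any side effects". VIII.2 likewise names salicylate as the only blood test there, then adds: "Subjects will also have serum salicylate concentrations measured at experimental visits 6 and 7".

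**Kidney and liver tests (VII.E.6).** At baseline, Visit 3 lists "Lipid panel, insulin, hs-CRP, salicylate, creatinine, AST/ALT (4.5 ml blood- light green PST tube". On treatment, Visit 7 lists "venous blood sample to measure serum salicylate, AST/ALT and creatinine (0.5 ml blood" and repeats these tests in its item c.

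**Calls (VII.E.6).** The one scheduled evening call is on Day 25: "Coordinator or research staff will call subject in the evening to remind subject to start 3-day dietary record". Under VIII.2, calls about side effects are made by the subject.

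**The concern.** Two inputs to the only aggregate harm review do not line up with the schedule meant to supply them. If safety visit means what the VIII.2 heading says, the creatinine and ALT/AST values attributed to such visits are not collected there. The telephone questionnaire cited for symptoms appears neither in the visit schedule nor in the list of forms in VII.E.4.

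What is at stake is mainly the subject who stops early. The symptom-triggered sample in VIII.2 measures salicylate. Electrolytes and urinalysis may be added if acidosis is suspected, but creatinine and ALT/AST are not mentioned. VII.E.7 says that subjects lost to follow-up will not be recontacted. Someone who leaves because of intolerance could therefore add no on-treatment kidney or liver value to the review, although that is a person the reviewer would particularly want to see. Eligibility allows creatinine up to about 2.2 mg/dl, so some subjects may start with limited renal reserve.

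**Working it through.** The plan states no figure to reproduce. The check compares the texts, with a little arithmetic.

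**1. Scheduled creatinine and ALT/AST, by time**

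| Visit | Timing | Creatinine and ALT/AST |
|---|---|---|
| 3 | baseline | listed |
| 5 | about Day 14 | not listed (salicylate only) |
| 6 | Day 26 to 34 or 35 | not itemised; probable, since its 68 ml total equals Visit 3's |
| 7 | Day 27-35 | listed |

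The experimental methods (item e on blood chemistries) also plan a basic metabolic panel after 4 weeks. The count of on-treatment time points is 0 before Day 26, then 1 or 2.

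**2. Position within the 28-35 days of dosing**

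- Day 26: 26/35 = 74% to 26/28 = 93% of the course.
- Day 14: 14/35 = 40% to 14/28 = 50% of the course.

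**3. Salsalate subjects who might leave (n = 20)**

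- XI.2 attrition of 15-20%: 0.15 × 20 = 3; 0.20 × 20 = 4.
- Arthritis study in VIII.1 (about 3 g/day for 3 weeks): 234/782 = 0.299; 0.299 × 20 ≈ 6.
- A small 2-week comparison in VIII.1 reported no side effects at 3.0 g/day, which would suggest about 0.

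These are expected counts at the assumed rates. At a true rate of 30%, the 97.5th percentile of a binomial count with n = 20 is 10, so 6 is not a ceiling. The documents give no dropout timing for this trial. Assuming that anywhere from none to all of those leaving do so before Visit 6, the expected number without a value is 0-3 or 0-4 at the XI.2 rates and 0-6 at the arthritis-study rate.

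**4. Is there blood for the tests at Visit 5?** Stated volumes for Visits 1, 3, 5, 6 and 7: 22.5 + 68 + 9 + 68 + 4.5 = 172 ml. This agrees with "GRAND TOTAL Blood drawn over course of study: 172 ml". Visit 5's 9 ml (two 4.5 ml PST tubes) is already counted. At Visit 3 a single 4.5 ml PST tube serves salicylate, creatinine, AST/ALT and three other tests. Extra scheduled blood needed: 0 ml.

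**5. Symptom sources.** Scheduled symptom calls in the visible text: 0. Actual sources: the side-effect log (VIII.2) and the surveys at Visits 5 and 6. The Visit 7 text lists no survey.

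**The case against.** The strongest reply is that this is loose wording. Item b speaks of safety visits in the plural and does not define them, and the VIII.2 paragraph under that heading goes on to Visits 6 and 7. If the term covers Visits 5-7, the promised tests exist for every completer, and item b does not say that every assay is run at every visit. The visit summary (Table 1) and the side-effect survey are attachments that are not in the documents. Two tubes for one assay at Visit 5 would be odd, so that line may be abbreviated. All of this stands, and it rules out inferring that the reviewer receives no on-treatment kidney or liver data.

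A reader might also infer that early leavers and symptoms are invisible to the reviewer. The documents do not support that: the report also covers reasons for attrition, dose reductions, compliance in reporting adverse events, and any safety issue in the period. Symptoms are recorded in the log and surveys.

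Nor do the documents show an early signal that would be missed. VIII.1 reports a small creatinine rise at 3.5 g/day in a 14-week trial. However, it reports no creatinine change after 4 weeks at 3-4 g/day, which is closer to this trial's dose and duration, and no change in liver function in the 14-week trial. Finally, for a completer, moving the first value from about Day 26 to Day 14 will seldom change which six-monthly report it enters.

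Two things survive: both descriptions of Visit 5 name salicylate alone, and nothing in the visible text gives an early leaver a creatinine or ALT/AST result.

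**Conclusion.** The point holds in a limited form. As written, there is no scheduled on-treatment creatinine or ALT/AST before about Day 26, which is 74-93% of the way through dosing, and a subject who leaves before then may have none. The telephone symptom source in item b matches nothing in the visible schedule.

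The number affected cannot be stated. About 3-4 of 20 salsalate subjects would be expected to leave at the plan's own attrition rate and about 6 at the arthritis-study rate, at any time during the study. The arthritis rate comes from a different population, and this trial reduces the dose before withdrawing a subject.

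The conclusion assumes that the Visit 5 text is complete and that the missing Table 1 adds no tests there. No efficacy analysis or sample size is affected. This is a cheap safety improvement, not a failure of the monitoring plan.

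**What to change.** 1. **VII.E.6, Visit 5:** add creatinine and ALT/AST, run on the two PST tubes already drawn.
2. **VIII.2:** add the same tests to any unscheduled or withdrawal sample. This is needed because Visit 5 cannot cover a subject who leaves before Day 14.
3. **VIII.4 item b:** name Visits 5-7 as the source of the safety laboratory values. Replace the telephone questionnaires with the side-effect log and the Visit 5 and 6 surveys.

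If Table 1 already lists these tests at Visit 5, the first change only brings the text into line. The rewording of item b is the minimum; alone it would be clerical and would leave early leavers without a value.

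**Cost:** about 30 randomised subjects × 3 tests = 90 assays, plus a few from unscheduled samples, and two or three lines of text. The 10 non-prediabetic controls do not attend Visit 5. No new visit, call or scheduled blood volume is needed.

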### X.4 How will information/data be collected and stored for this study (check all that apply):

- Paper/hard copy records (hard copy surveys, questionnaires, case report forms, pictures, etc.) - All hard copies of records will not contain any personal identifiers but only an individual subject code. Folders will be kept in a folder to keep out of public view when transported from CRU to the coordinagtors office. Data folders will contain hard copies of data capture forms such as surveys and data collected during experimental visits. All data folders will be kept in folder and locked in storage cabinet in the coordinators office (C-44 GH). The office is locked when the coordinator is not in the office. Signed informed consent documents and will be kept in a separate folder in a different locked file cabinet in the office.
- Electronic records (computer files, electronic databases, etc.) Data will be
  entered using subject ID code into the ICTS REDCap web-based database
  application that is password protected. No personal identifiable data will be
  entered. Only research staff on the IRB approved study will be allowed access
  this database. The ICTS REDCap staff are responsible for maintaining security
  of the data. Some data using subject ID code will also be entered into a
  Microsoft Excel and SPSS datasheets that will be kept in a shared server for

CLAS that is password protected. Only research staff on the IRB approved study will have access to the folder the study on the server. This server is maintained by [name], IT Support Services, College of Liberal Arts and Sciences.

- Name [name]
- Title IT Support Services II, College of Liberal Arts and Sciences
- University/VA Job Classification IT Support Services II
- Biologic samples (blood draws, check swabs, saliva samples, tissue samples, etc.) Basic blood chemistries will be sent to the UIHC pathology lab for analysis. Remaining biological specimens such as blood, endothelial cells, and DNA will be labeled with subject code, date collected and IRB protocol number and transported from the CRU to the PIs laboratory (522 Field House) in a secure unbreakable biohazard container. Samples will be stored in the PIs laboratory in a -80C freezer in N400 FH. All samples will be labeled with date collected and subject ID code only. No personal identifiable information will be labeled on the sample. Only the PI and his research staff will have access to the samples.
  - Name [name]
  - Title Assistant Professor
  - o University/VA Job Classification Assistant Professor

### X.5 Do the confidentiality protections indicated above allow only members of the research team to access the data/specimens?

Yes

### XI. Data Analysis

### XI.1 Describe the analysis methods you will use, including, if applicable, the variables you will analyze

Statistical analyses. To determine if differences in outcomes are present at baseline between obese pre-diabetic vs. non-pre-diabetic groups, an independent two-sample t-test will be performed. To determine if baseline (pre-intervention) differences exist between salsalate and placebo prediabetic groups after randomization, independent two-sample t-tests will be performed. To test the main hypotheses, a repeated measures ANOVA will be performed in which treatment (salsalate vs. placebo) is the between-subjects factor, and time (pre- vs. post-intervention outcomes) is the within-subjects factor for the primary dependent variables. The critical test for the dependent variable will be the interaction between the within-subjects and betweensubjects factors. Tests for mean contrasts will be used to compare variables of interest pre vs. post Salsalate or placebo. Based on a previous study, we expect small reductions in fasting glucose, triglycerides, LDL cholesterol and possibly systolic blood pressure after Salsalate treatment. Covariates (e.g., variables that change after Salsalate) will be included into the mixed model. Bivariate pearson correlation analysis will be performed on the change in each dependent variable and aforementioned selected covariates after Salsalate.

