## VI.6 How many minor subjects do you expect to consent or enroll for this project?

### VI.13 Describe EACH of your subject populations

- Include description of any control group(s)
- Specify the Inclusion/Exclusion criteria for EACH group

A total of 30 healthy men and women ages 18-49 years who are obese defined as body mass index (BMI) of 30 kg/m2 or greater and with prediabetes (defined as fasting blood glucose between 100-126 mg/dl, a fasting blood glucose of 140-199 mg/dl at 120 min during an oral glucose tolerance test; or HbA1C of 6-6.5%) will be enrolled and randomized to 4-5 weeks of salsalate or placebo in the study. CONTROL GROUP: Another n=10 healthy obese men and women age 18-49 WITHOUT prediabetes will be enrolled for baseline testing but will not undergo randomization to the salsalate/placebo intervention. Therefore, total enrollment will be n=40.

All subjects will have no history of cardiovascular, metabolic or pulmonary disease as determined from medical history and physical exam, and a resting 12-lead ECG. Subjects may be on anti-hypertensive medications but will be asked to hold the medication on the morning of testing. Subjects on medications for Type I or II diabetes mellitus or for hyperlipidemia will be excluded (see complete list below). Subjects will be non-smokers or quit smoking at least one year ago. Women will have regular menses and will be tested during the early follicular phase of their menstrual cycle (within 8 days of onset of menses) to control for differences in circulating estradiol concentrations.

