### VII.E.1 Will subjects be randomized? Yes

VII.E.1.a Will any subjects be blinded to which study arm they have been assigned?

Yes

VII.E.1.b Does the protocol permit telling subjects their treatment assignment at the end of the entire study?

Yes

VII.E.1.c Describe the circumstances under which subjects will be told what study arm they have been assigned.

At the end of the study, or after an adverse event that the subject is withdrawn from the study.

VII.E.2 Describe randomization scheme/assignment including ratio such as 1:1, 2:1 etc.

Subjects will be randomized 2:1 to salsalate or placebo, respectively so their is 2/3 chance they will be randomized to salsalate and 1/3 to placebo. This scheme was chosen to ensure proper effect sizes can be determined in the salsalate group in this pilot study. The obese non-prediabetc group will not be randomized and only undergo baseline testing.

VII.E.3 Will any questionnaires, surveys, or written assessments be used to obtain data directly from subjects in this study?

Yes

VII.E.4 List all questionnaires, surveys, written assessments and ATTACH each one to the application. (NOTE: You are NOT prohibited from attaching copyrighted materials to this application)

Phone screening questionnaire
Demographics and Contact Info questionnaire
Health History questionnaire
Modifiable Activity Questionnaire (MAQ)

3 Day dietary record (CRU bionutrition)

Salsalate screening log

VII.E.5 Does this project involve creating any audiotapes, videotapes, or photographs?

No

VII.E.6 Provide a detailed description in sequential order of the study procedures following the consent process - DO NOT cut and paste from the Consent Document.

Describe study populations separately if they will be participating in different procedures - include CONTROL population if applicable.

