#### **DESCRIBE:**

- What subjects will be asked to do/what happens in the study (in sequential order)
- The time period over which procedures will occur
- The time commitment for the subject for individual visits/procedures
- Long-term followup and how it occurs

Experimental design. A total of 30 obese (defined as body mass index >30 kg/m2) adults age 18-49 years with prediabetes will be enrolled and randomized to 4-5 weeks of Salsalate or placebo in a randomized (2:1), double-blind, placebo controlled, parallel study design. Subjects will orally ingest 3000 mg/day (1500 mg in a.m. and 1500mg in the p.m.) of Salsalate (n=20) or placebo (n=10) for 28-35 days. A total of n=10 obese NON-prediabetic CONTROL subjects will be enrolled to establish prediabetes-related differences in obese adults primary outcomes at baseline. Therefore, a total of 40 subjects will be enrolled. The non-prediabetic control subjects will undergo screening (Visits 1 and 2) and baseline experimental testing (Visits 3, 4) but will NOT undergo the Salsalate/placebo intervention or visits 5, 6 or 7. Prediabetes will be defined as fasting (at leaset 8 hour fast) blood glucose between 100-126 mg/dl, a fasting blood glucose of 140-199 mg/dl at 120 min during an oral glucose tolerance test, or HbA1C between 6.0 – 6.5%.

Order of visits. Subjects will undergo experimental testing at baseline and again after the 4-5 weeks of Salsalate or placebo. Subjects will be studied between 7:00 and 10:00 am in the Clinical Research Unit (CRU) in the Institute for Clinical and Translational Science (ICTS) at the University of Iowa following an 8 hour overnight fast. The order of visits are as follows and will occur over a period of 7-8 weeks (see TABLE 1 attachment for summary of visits):

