### XI.2 Provide the rationale or power analysis to support the number of subjects proposed to complete this study.

Sample size calculations. Sample sizes were calculated based on 80% power at an alpha level of 0.05. Estimated effect sizes for Aim 1 were used for final sample size calculation for obese prediabetic subjects because carotid-femoral PWV is the primary outcome and has the smallest effect size (d) in pilot data of 4 days before vs. after Salsalate. A sample size of 16 subjects per group was determined based on the d of 1.06, based on mean difference in carotid-femoral PWV (-1.0  $\pm$  1.0 m/sec) after Salsalate vs. Placebo.

With a conservative estimated attrition rate of 15-20% and the 2:1 randomization, a total of 20 subjects will be assigned to the Salsalate group, and 10 subjects to the placebo group was determined to be required for the study (total sample size=30). A

sample size of 12 for Aim 2 (FMD) was determined from d of 1.2 for a mean difference in FMD of  $\pm$  2.2 after 4 days Salsalate vs placebo based on previously published work by the PI (19). Because the effect sizes for Aim 1 and 2 are based on preliminary data of 4 days of Salsalate treatment and our proposed study is 4 weeks, we predict that the actual effect sizes will be slight higher because of the longer duration of treatment. Therefore, the proposed study will help determine actual effect sizes for chronic Salsalate therapy for a future larger randomized clinical trial.

A total of 10 obese non-prediabetic control subjects will be recruited to established differences in main outcomes at baseline but will NOT undergo randomization or salsalate/placebo treatment period.

Therefore, total sample size to be enrolled is 40.

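### The baseline prediabetic v non-prediabetic comparison (30 v 10) is an unadjusted t-test on non-randomised groups with no stated matching, so any systematic age, sex or BMI difference would bias it

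*Combined protocol and SAP*

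**What the plan says.** Section VI.13 sets up the control group: "Another n=10 healthy obese men and women age 18-49 WITHOUT prediabetes will be enrolled for baseline testing". Section VII.E.2 confirms its status: "The obese non-prediabetc group will not be randomized and only undergo baseline testing". The experimental design in VII.E.6 gives the purpose, namely that "obese NON-prediabetic CONTROL subjects will be enrolled to establish prediabetes-related differences in obese adults primary outcomes at baseline", and XI.2 repeats it without a sample-size justification for the 10.

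The analysis is one sentence in XI.1: to determine whether "differences in outcomes are present at baseline between obese pre-diabetic vs. non-pre-diabetic groups, an independent two-sample t-test will be performed". No covariate is named for this test. The only covariate sentence in XI.1 is "Covariates (e.g., variables that change after Salsalate) will be included into the mixed model". It belongs to the salsalate v placebo model and cannot apply to controls, who have baseline data only. No section describes matching or balancing the controls on age, sex or BMI.

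**The concern.** The comparison is observational, and its stated purpose is to show differences related to prediabetes. An unadjusted difference in means combines any effect of prediabetes with the effect of anything else that differs systematically between the groups. Carotid-femoral PWV, FMD, sympathetic nerve activity and baroreflex sensitivity may each vary with age, sex and adiposity.

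The plan recognises this kind of problem elsewhere. VI.13 fixes menstrual phase in women to control estradiol differences, and the dietary-record paragraph of VII.E.6 notes that diet could affect comparisons between subjects. Neither consideration reaches the test in XI.1.

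At stake is the interpretation of the only planned comparison that uses a quarter of enrolment (10 of 40). These controls attend Visits 1 to 4, which include brachial artery catheterisation.

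**Working it through.** **The plan's own figure.** The documents give no power or sample-size figure for 30 v 10. Their 16 per group (XI.2) is for salsalate v placebo. At two-sided 0.05 and 80% power, d = 1.06 gives 14 per group (normal approximation) or 15 (t-test), and d = 1.0 gives 16 or 17. The 16 is therefore reproduced to within 2, but it does not bear on this comparison.

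**Inputs from the documents.** n1 = 30 and n2 = 10 (VI.13, VII.E.6). Age is 18 to 49, a span of 49 − 18 = 31 years. BMI is at least 30 kg/m² with no upper limit (VI.13). Alpha is 0.05 (XI.2; taken as two-sided).

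**Assumed inputs, not in the documents.** g is the systematic difference between groups in one covariate, in SD units. r is the within-group correlation of that covariate with the outcome.

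**Sensitivity of the planned test.** With df = 30 + 10 − 2 = 38 and noncentrality d × sqrt(30 × 10 / 40) = 2.739 d, 80% power needs d = 1.05. Power at d = 0.5 is 27%.

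**Bias and false-positive rate.** With no true prediabetes effect, the expected unadjusted difference is r × g outcome SDs, and the noncentrality is 2.739 × r × g:

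| g (SD) | r | Bias r × g (SD) | Rejection rate at nominal 5% |
|---|---|---|---|
| 0.5 | 0.3 | 0.15 | 6.9% |
| 0.5 | 0.5 | 0.25 | 10.2% |
| 1.0 | 0.3 | 0.30 | 12.6% |
| 1.0 | 0.5 | 0.50 | 26.6% |

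Over the wider grid of g from 0.25 to 1.0 and r from 0.2 to 0.6, the rate runs from 5.2% to 36.0%. In the last row of the table, the test rejects for pure confounding as often as it would detect a true effect of 0.5 SD.

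**Does adjustment work at n = 40?** A simulation with 8,000 runs per scenario fitted group plus three covariates (40 − 5 = 35 residual df). One covariate was shifted by g and the other two were noise. Under these four scenarios and one with no imbalance, the adjusted test rejected in 4.8% to 5.5% of runs, with bias within 0.01 SD of zero.

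**Effect on precision.** Let R² be the share of outcome variance explained by the covariates. The ratio of adjusted to unadjusted SE is about sqrt[(1 − R²) × (38/35) × VIF]. For a 1 SD shift in one covariate, VIF = 1 + (0.75 × 0.25) × 1² = 1.1875. An assumed R² of 0.2 gives sqrt(0.8 × 1.0857 × 1.1875) = 1.02, and 0.4 gives sqrt(0.6 × 1.0857 × 1.1875) = 0.88. The interval can become slightly wider or narrower.

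**The case against.** Several counter-arguments have force.

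- **Shared restrictions.** Both groups are aged 18 to 49, obese, non-smoking, without cardiovascular disease and off lipid and diabetes drugs, and women are tested in the early follicular phase. This reduces confounding. It does not remove it, because wide age and BMI ranges remain. The answers on the percentages of men and women are not legible in the available text, so nothing is inferred about the planned sex mix.
- **Place in the study.** The comparison is in neither Aim 1 nor Aim 2. It does not touch the treatment-by-time interaction that XI.1 calls critical, and this is a pilot. That lowers the weight of the point.
- **Wording of the purpose.** Prediabetes-related can be read as association, and an unadjusted test can describe a difference between groups. This stands, so it is too strong to say that the control group cannot answer its question, or that age, sex and BMI differences will be taken for effects of prediabetes.

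Three stronger readings are tempting but unsupported. First, a reader might treat chance imbalance as bias. With 30 v 10, the SE of a standardised covariate difference is sqrt(1/30 + 1/10) = 0.365 SD, so differences up to about 1.96 × 0.365 = 0.72 SD arise by sampling alone. If the groups share one covariate distribution, that variation is already in the SE of the t-test and its error rate stays near 5%. Only a systematic difference biases it. Second, a reader might judge confounding in PWV against the 1.0 m/s in XI.2. That is a salsalate v placebo effect. The documents give no expected cross-sectional difference and no slope of PWV on age. Third, a reader might expect adjustment to sharpen the estimate reliably. The SE ratios above show that it may not when the groups differ.

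**Conclusion.** The point holds as a modest analysis weakness. The test is unadjusted, the groups are not randomised, no matching is stated, and the result is meant to speak to prediabetes. Any systematic difference in age, sex or BMI would therefore bias the estimate, in either direction.

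The 7% to 27% range rests wholly on the assumed g and r for a single covariate. The documents supply neither and do not show that such an imbalance will occur. With several covariates, the biases could add or cancel. The conclusion is confined to this supporting baseline comparison.

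**What to change.** In XI.1, replace the t-test for prediabetic v non-prediabetic subjects with a linear model for each outcome containing group, age, sex and BMI, fixed before the data are seen. Report the adjusted difference with its 95% CI as the main result and the unadjusted difference beside it. Tabulate age, sex and BMI by group so that readers can judge overlap, because with 10 controls the adjustment leans on linearity if overlap is poor. Describe the result as an association, since unmeasured confounding remains.

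The cost is a sentence or two in XI.1. Age and sex are recorded at screening (VII.D.20, VII.D.22), and height and weight are measured at Visit 1 (VII.E.6), so no new data, visits or subjects are needed. The statistical price is three degrees of freedom (38 to 35) and possibly a slightly wider interval if the groups differ on the covariates.
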